The treatment plan is performed with the Raystation clinical treatment planning software by a Medical Physicist from the EBAMed team. An electrophysiologist from the San Matteo team will draw on the CT the contours of a realistic ventricular tachycardia ablation treatment target and the contours of relevant organs-at-risk (including e.g. adjacent cardiac substructures, oesophagus, stomach and trachea). An additional virtual structure will be contoured on the CT, representing the position of the ultrasound probe (based on the best probe view as assessed by scoring for the primary endpoint). A successful treatment plan will need to accomplish all of the following:

- radiation beams do not go through the ultrasound probe
- treatment target receives at least 25 Gy (typical treatment dose)
- organs at risk receive a dose below the threshold given in Table 1

Table 1: OARs and their relevant metrics (some taken from literature¹, others from consultations with early implementers).

OAR	Relevant Metric	Limit
Whole heart – PTV	*D(50%Volume)	< 5 Gy
Non-involved myocardium = Left ventricular wall + right ventricular wall – PTV	V(20Gy)	Low as possible
Left Atrium	*Dmax	< 4.4 Gy
Mitral valve	Dmax	< 14 Gy
Aortic valve	Dmax	< 14 Gy
Left-anterior-descending coronary artery	*Dmax	< 14 Gy
Aorta	*Dmax	< 20 Gy
Superior Vena Cava	*D(50%Volume)	< 0.6 Gy
Whole Lungs	*V(total) – V(7Gy), D(5%Volume)	> 1500 cc
Spinal Canal	*Dmax V(6Gy)	< 7 Gy < 0.1cc
Oesophagus	*Dmax V(9Gy)	< 14.5 Gy < 1cc
Skin	*Dmax V(10Gy)	< 14.4 Gy < 10 cc
Trachea	*Dmax V(10Gy)	< 15 Gy < 1 cc
ICD (electronics)	*Dmax	< 0.5 Gy

Data that may influence the results will be collected such as patient’s demographics and cardiovascular history.

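### Secondary endpoint: if 25 Gy is a whole-target minimum, a target overlapping a Dmax-limited structure cannot score 1, and that zero is pooled with probe-caused zeros

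*Protocol*

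**What the plan says.** Protocol section 2.2 gives the secondary objective as the theoretical impact of where the probe sits, studied by hypothetical treatment planning in patients who have a full field of view CT. A patient scores 1 if a plan that respects the dose constraints can be made, and 0 if it cannot. The result is the percentage scoring 1 among those scored.

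The same section defines success as a joint rule: "A successful treatment plan will need to accomplish all of the following". Three conditions are then listed:

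- The first concerns the probe: "radiation beams do not go through the ultrasound probe".
- The second sets a dose floor for the target: "treatment target receives at least 25 Gy (typical treatment dose").
- The third points to the table of limits: "organs at risk receive a dose below the threshold given in Table 1".

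Table 1 removes the PTV from two rows. One is "Whole heart – PTV"; the other, for the ventricular walls, is "Non-involved myocardium = Left ventricular wall + right ventricular wall – PTV". The rows for the left atrium, mitral valve, aortic valve, "Left-anterior-descending coronary artery" and aorta have a Dmax limit and no such subtraction.

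An electrophysiologist draws both the target and the "relevant organs-at-risk (including e.g. adjacent cardiac substructures, oesophagus, stomach and trachea"). The section gives no rule for an organ at risk that shares tissue with the target.

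**The concern.** Two of the three conditions can pull against each other in the same tissue. One sets a floor on dose inside the target, and the other sets a ceiling on the maximum dose to certain cardiac structures and the aorta. Where a target and such a structure overlap, the floor lies above the ceiling, so the score is settled by where the hypothetical target was drawn, before any beam or probe is considered.

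This matters because only the first condition involves the probe. Score 0 is given for any failure to make a plan, whatever the cause, and no comparison plan without the probe is described. A zero that comes from the target's location therefore looks the same as a zero that comes from the probe, and the proportion mixes the two. The group is small: at most 24 patients are planned, and only those with a CT are scored.

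**Working it through.** **Plan's own figure.** The Protocol states no expected value or precision for the secondary endpoint, so there is none to reproduce. The lower limits of 73% and 79% in section 4.1 concern the primary endpoint. Exact Clopper-Pearson limits for 22/24 and 23/24 are 73.0% and 78.9%, so they reproduce, but they play no part here.

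**Step 1: inputs, all from section 2.2.** The target dose condition is at least 25 Gy. The Dmax limits without PTV subtraction, for cardiac structures and the aorta, are:

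| Structure | Dmax limit | Required in shared tissue | Possible? |
|---|---|---|---|
| Left atrium | < 4.4 Gy | ≥ 25 and < 4.4 Gy | No |
| Mitral valve | < 14 Gy | ≥ 25 and < 14 Gy | No |
| Aortic valve | < 14 Gy | ≥ 25 and < 14 Gy | No |
| Left anterior descending artery | < 14 Gy | ≥ 25 and < 14 Gy | No |
| Aorta | < 20 Gy | ≥ 25 and < 20 Gy | No |

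The remaining Dmax limits in the table (spinal canal, oesophagus, skin, trachea, ICD) run from 0.5 to 15 Gy, so the same logic would apply to them if a target ever overlapped them.

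**Step 2: what the impossibility depends on.**

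- The 25 Gy must hold at every point of the target. That is the plain reading, but no coverage metric is given. If only a stated percentage of the target had to reach 25 Gy, a very small overlap could pass.
- The row must have a Dmax limit. Rows limited only by volume, such as the superior vena cava (dose to 50% of its volume) and the lungs, can be met despite an overlap.
- The target must actually overlap the structure. Lying next to it is not enough.

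**Step 3: effect on the proportion.** Let m be the number of patients with a CT and k the number whose target overlaps a Dmax-limited structure. All k score 0, so the highest attainable proportion is (m - k)/m = 1 - f, with f = k/m. Neither m nor k is in the Protocol, so the values below are assumptions:

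| k | m = 12 | m = 24 |
|---|---|---|
| 0 | 12/12 = 100% | 24/24 = 100% |
| 1 | 11/12 = 92% | 23/24 = 96% |
| 3 | 9/12 = 75% | 21/24 = 88% |
| 5 | 7/12 = 58% | 19/24 = 79% |

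Each overlap lowers the ceiling by 1/m. Since m is at most 24, that is at least 1/24 = 4.2 points; with m = 12 it is 1/12 = 8.3 points.

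**Step 4: what separate reporting would show.** With s successes, the pooled proportion is s/m and the proportion without overlap patients is s/(m - k). Taking m = 12, k = 3 and s = 8 as an illustration, these are 8/12 = 67% and 8/9 = 89%. The first mixes target location with planning difficulty. The second has the forced zeros removed.

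**The case against.** The strongest reply is that the problem is conditional and that the Protocol does not show the condition arising. The contoured substructures are described as adjacent to the target, not inside it. The target is hypothetical and meant to be realistic, and nothing says it will include atrium, valve, artery or aorta. The overlap count could be zero. This stands: the size is unknown, and the caps above are only 1 - f under assumed values.

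A reader might infer that the missing PTV subtraction in the other rows is a mistake. The Protocol does not support that. A ventricular target would normally lie within the whole heart and the ventricular walls, so those two rows have an ordinary reason to subtract it, while the other structures need not contain the target. What is missing is a rule for the case where they do.

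A reader might also infer that the different limits for the left atrium and mitral valve conflict, or that the drop from 25 Gy to the lower limits at a border cannot be achieved. Neither follows. One plan can meet different limits for different organs, and an organ-at-risk limit below the target dose does not itself show that planning is infeasible.

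Some metrics carry an asterisk whose meaning is not visible in the text at hand, and one row asks only that a volume be kept low, which is not a pass/fail threshold. The point does not rest on either. The two valve rows carry no asterisk and have numerical limits.

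Finally, any planning failure unrelated to the probe blurs the endpoint, not only overlap. That is correct. Recording overlap removes only the zeros that are certain beforehand.

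**Conclusion.** The point holds in a conditional form. Under a whole-target reading of the 25 Gy condition, a target that overlaps a structure with a plain Dmax limit cannot score 1 wherever the probe is placed, and the endpoint does not separate that zero from one the probe caused. The proportion is then capped at 1 - f, where f is the unstated share of CT patients with such an overlap.

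It would go too far to say that overlap with any listed structure fails automatically, or that the endpoint is bound to be distorted. Volume-limited rows are unaffected, a percentage-coverage reading could let a very small overlap pass, and f may be zero.

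Severity is minor. This is a descriptive secondary endpoint in the CT subset of a one-arm feasibility study, with no success threshold or test attached to it, and the primary endpoint is untouched.

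**What to change.** Before planning starts, the sponsor's clinicians and physicists should reconcile the 25 Gy condition with the Dmax rows of Table 1. They should state how tissue shared by the target and a Dmax-limited structure is scored, and whether 25 Gy is a minimum over the whole target or a coverage criterion. Which limit or rule applies is for them to decide and is not proposed here.

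At contouring, before beams are set, record for each planned patient whether the target overlaps a Dmax-limited structure, and which one. The text uses target in the dose condition and PTV in the table without saying whether they are the same volume, so the record should name the volume used.

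Report the secondary proportion with its 95% CI both with and without the overlap patients, together with their number.

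The cost is a clarified table, one extra field per planned patient, and a second proportion on a smaller denominator with a correspondingly wider interval. No new patients or procedures are needed.

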2.3 Project design

This is a single center, one arm, feasibility study. The patients will undergo one Cardiac motion monitoring procedure to collect ultrasound imaging data via the Demonstrator 2 developed by EBAMed SA, Switzerland and there is no follow-up planned.

2.4 System in use

For this study, Demonstrator 2 and related components provide monitoring of the cardiac motion in all its components: cyclical heart-beat motion, cyclical respiratory motion and non-cyclical heart position changes with the patient lying in supine position.

¹ Radiosurgery for ventricular tachycardia: preclinical and clinical evidence and study design for a German multi-center multi-platform feasibility trial (RAVENTA). Oliver Blanck et al. Clinical Research in Cardiology (2020) <https://doi.org/10.1007/s00392-020-01650-9>

The system encompasses Demonstrator 2 for ultrasound imaging and optical localization. The system offers non-invasive means for accurate and precise real-time monitoring of the patient's heart position and cardiac motion management (see **Figure 1** below).

[figure not shown]

Figure 1 Schematic view of study system

The system is comprised of the following functional components:

- The Workstation, which integrates:
 - Consumer grade computer
 - Consumer grade screen
 - Consumer grade keyboard and mouse

The Workstation is used for:

- Communication with Optical localization system
- Communication with Demonstrator 2
- Graphical User Interface
- The real-time data acquisition module of Demonstrator 2 (Appendix A - Demonstrator IFU), which controls data acquisition from:
 - ECG system (Appendix B – ECG Operator’s Guide)
 - Ultrasound imaging system (beamformer and probe)
- The Optical localization system (Appendix C - Optical Localization System User Guide)

The following additional components are provided to the users:

- Disposable ECG electrodes
- Re-usable reflective markers for optical localization
- Disposable ultrasound probe holder strap
- Re-usable ultrasound probe holder
- Patient positioning board with grab bar and arm support (EagleBoard)

The system provides the following output information:

- User Interface with live ultrasound images, ECG signals including ECG R-waves, ultrasound probe localization data and metrics calculated during the data acquisition, as well as warnings.
- Session records including ultrasound images, ECG data and ultrasound probe localization data.
- Metrics calculated during the data acquisition, including warnings

3 STUDY POPULATION AND PROCEDURES

3.1 Study population, inclusion and exclusion criteria

The study will enrol up to 24 adult patients diagnosed with ventricular tachycardia.

Patients with cardiac or non-cardiac implants in the thorax area are of interest for the research.

Patients of all relevant ages and gender should be represented in the final study population.

Inclusion criteria:

1. Patient with history of ventricular tachycardia
2. Over 18 years old
3. Ability and willingness to provide written informed consent

Exclusion criteria:

1. Patient in arrhythmic storm

3.2 Recruitment, screening and informed consent procedure

All consecutive adult patients diagnosed with ventricular tachycardia and visiting the site will be screened for the study by the study leader and his study team.

After reviewing the information sheet, patients will be offered the opportunity to ask questions and they will be offered enough reflexion time before they sign the informed consent form. Two copies of the informed consent will be signed. One copy is for the patient, one copy will be maintained at the site. The data collection and study procedure will start after the signature of the informed consent by both parties and within a maximum of 30 days after the signature. Above 30 days, a new consent form needs to be collected before proceeding with the protocol.

The patients will not receive compensation for their participation in the study.

3.3 Study procedures

Patient's participation starts at informed consent signature and ends after completion of the study's Cardiac Motion Monitoring procedure.

The study will start as soon as the protocol is approved by ethics. The recruitment period is expected to last from May 2021 to August 2021.

The table below describes the data collection and study procedures:

Data Collection	Information and informed consent form	Procedure (within 30 days of consent)
Signature	X	
Demographics and cardiovascular history		X
Cardiac Motion Monitoring with Demonstrator 2		X
CTscan (if available)		(X)
Adverse Event		X
Deviations, technical issues		X

3.1.1 Demographics and cardiovascular history

The patient will be asked to confirm his/her demographics and cardiovascular history.

3.1.2 Cardiac Motion monitoring

The following procedure steps will take place:

- The study system is installed in the room before patient arrival
- The patient needs to *fully* undress the upper body before lying on the bed
- The 3 ECG electrodes are placed
- Ultrasound gel is applied on the ultrasound probe

A – Apical view

- The ultrasound probe is positioned for apical viewing and fixed with the probe holder and the probe holder strap around patient's chest. Probe position is recorded on case report form. The relative position of the probe is automatically recorded via is optical localization system.
- The cardiac motion monitoring can start. During data acquisition, the image quality of the ultrasound images is visually monitored. The following data sequences are acquired successively:
 1. Patient in free breathing, 5 minutes
 2. Next 5 minutes, the patient starts holding breath for 10 seconds, repeated every minute (total: 5 breath holds in 5 minutes)
- Ultrasound probe, probe holder and strap are removed

B – Parasternal view

- The ultrasound probe is positioned for parasternal viewing and fixed with the probe holder – when available and stable - or held manually.
- The following data sequences are acquired successively:
 1. Patient in free breathing, minimum 1 minute, goal: 5 minutes with fixed probe position
 2. Next 5 minutes, the patient starts holding breath for 10 seconds, repeated every minute (total: 5 breath holds in 5 minutes), with fixed probe position. Note: this step is required when probe holder is in use, and optional when probe is manually held.
- The patient is offered tissues to remove ultrasound gel before dressing up
- The patient is asked whether he/she experienced any discomfort during the procedure

The procedure is performed by a trained investigator. The Cardiac Motion monitoring procedure will last for up to one (1) hour.

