1 BACKGROUND AND PROJECT RATIONALE

Echocardiography is an established specialty with dedicated tools, which require a lot of know-how both in manipulation and interpretation [1, 2]. Most cardiac patients who are prescribed a Computed Tomography scan (CT scan), or a Magnetic Resonance Imaging exam will undergo transthoracic echocardiography in the first place. The Prospective Cardiac Ultrasound Imaging Study aims at collecting cardiac ultrasound data from patients diagnosed with ventricular tachycardia. The research will analyse the ultrasound image data quality and establish if it is appropriate to develop a new medical device supporting automated cardiac ultrasound image interpretation during non-invasive cardiac procedures, i.e. ventricular tachycardia stereotactic radioablation. Such device would allow for a new way of monitoring patients during hospital procedures.

This early research protocol will collect data from volunteer patients. The data will not be used for diagnostic nor treatment purposes and the protocol's procedure duration is limited, hence the research is of very limited risk for the participants. The research has the potential to enable the creation of a medical device that will benefit patients with ventricular tachycardia and other cardiac pathologies in the future.

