2.2 Primary and additional endpoints

Objectives

The primary research objective is the proportion of subjects who have a positive evaluation in image interpretation metric and positive visual inspection of the ultrasound images.

Secondary objective; Additionally, for patients for whom a full field of view CT scan is available, the theoretical impact of probe positioning during a CT scan is analysed for hypothetical treatment planning.

Endpoints

Primary

The objective will be quantitatively assessed by scoring each patient as follows:

- A) Cardiac motion analysis performance:
 - o Score 1 if analysis of the ultrasound images with the EBAMed software gives a cardiac phase error (within R-R interval) < 0.1
 - o Score 0 otherwise
- B) Respiratory motion analysis performance:
 - o Score 1 if analysis of the ultrasound images with the EBAMed software gives a motion amplitude lower than 30 mm and if the number of breathing cycles matches the one observed from the motion of the chest.
 - o Score 0 otherwise

- C) Image quality performance:
 - o Score 1 if visual inspection by a member of San Matteo team can identify in the ultrasound images at least one of these structures: left ventricular wall, interventricular septum, or heart valve.
 - o Score 0 otherwise
- D) Image quality performance :
 - o Score 0 if visual inspection by a member of San Matteo team identifies that the heart becomes invisible for part of the time due to tissue motion linked to respiration.
 - o Score 1 otherwise

For each patient, scoring will be done for each imaging view (parasternal and apical). If the score is 2 (at least 1 point in A or B and 1 point in C or D) or higher for at least one of the imaging views, the outcome will be considered as positive. The final result will be the proportion (in %) of patients with a positive outcome defined as the number of patients with a positive evaluation divided by the total number of patients x 100.

Secondary

The objective will be quantitatively assessed by scoring each patient (only those with a CT available):

- with Score 1: if a successful radio-ablation treatment plan respecting dose constraints can be created using a clinical treatment planning software (see details below) and,
- with Score 0: if it is not possible to create such a treatment plan .

The final result will be the proportion of patients (in %) with a 1 Score: number of patients with score 1 divided by the number of patients with Score 0 or 1 x 100.

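### Does allowing a hand-held parasternal probe, with no required note of how it was held, undermine the primary or secondary result?

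*Protocol*

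**What the plan says.** The acquisition rules are in section 3.1.2 of the protocol.

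- **Apical view (part A).** The probe is fixed with holder and strap; no manual option is given. There are 5 minutes of free breathing, then 5 minutes with 5 breath holds. "Probe position is recorded on case report form", and the optical system records the relative position automatically.
- **Parasternal view (part B).** The holder is used "when available and stable - or held manually". Free breathing lasts "minimum 1 minute, goal: 5 minutes with fixed probe position". Of the breath-hold sequence, the protocol says that "this step is required when probe holder is in use, and optional when probe is manually held". Part B does not repeat the sentences on the case report form and optical recording.

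Section 2.2 scores the two views separately. If the score is 2 "or higher for at least one of the imaging views, the outcome will be considered as positive". For the secondary endpoint, the virtual probe is drawn on the CT "based on the best probe view as assessed by scoring for the primary endpoint".

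Section 2.4 lists the system's output without distinguishing views: "Session records including ultrasound images, ECG data and ultrasound probe localization data". Section 7.2 has these records saved and archived. The table in section 3.3 provides for collecting deviations and technical issues.

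**The concern.** The two views are acquired to different standards, yet they count equally. A patient could fail on the strapped apical view, pass on a short hand-held parasternal view, and be a primary success. The same view could then fix the plan geometry.

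Section 1 gives the purpose as a device for "automated cardiac ultrasound image interpretation during non-invasive cardiac procedures", namely stereotactic radioablation. A reader may reasonably ask how many successes came from a probe that stayed in place without an operator. Section 2.3 provides one procedure and no follow-up, so a fact not noted on the day may be lost. Hand-holding is permitted, so it would not be logged as a deviation. At stake would be the reading of the headline proportion: with 24 patients, a few hand-held-only successes would visibly lower a holder-only figure.

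**Working it through.** **1. The plan's own figure.** Section 4.1 gives lower 95% limits of 73% for 22/24 and 79% for 23/24. The exact (Clopper-Pearson) lower limit is the 0.025 quantile of Beta(x, n − x + 1).

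- x = 22, n = 24: 73.0%.
- x = 23, n = 24: 78.9%.

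Both agree with the protocol.

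**2. Can one view decide the outcome?** Yes. Within a view, success needs a point in A or B (3 of 4 combinations) and a point in C or D (3 of 4), so 3 × 3 = 9 of the 16 patterns are positive. No condition refers to the other view or to how the probe was held. The factual premise is right.

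**3. What do the required data already show?** Define:

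- a = patients positive on the apical view, all holder-fixed under part A;
- p = patients positive on the parasternal view only;
- h = those among p whose parasternal probe was hand-held.

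Then primary successes = a + p, and successes with a holder-fixed view = a + p − h. Since 0 ≤ h ≤ p,

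a ≤ holder-fixed successes ≤ a + p.

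Both a and p come directly from the per-view scores that section 2.2 requires. If every success is apical-positive, p = 0 and so h = 0. A count of 0/24, with exact upper 95% limit 1 − 0.025^(1/24) = 14.2%, could then be reported without any extra field.

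**4. The breath holds narrow it further.** Split p into p₀ (no parasternal breath holds) and p₁ (breath holds done). With the holder in use, breath holds are required, so a session without them is either hand-held or a deviation, and section 3.3 collects deviations. Leaving deviations aside, p₀ ≤ h ≤ p₀ + p₁. Only the p₁ patients are unresolved.

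**5. The secondary endpoint.** A plan built on the apical view uses a holder-fixed position. Only parasternal-based plans leave the question open. Whether a beam crosses the drawn probe depends on where the probe is, not on what holds it, so the score is the same either way.

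**6. Size, if such patients exist.** The documents give no rate. Assume k of the 22 target successes are hand-held-only (exact 95% intervals):

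| k (assumed) | Positive on a holder-fixed view | 95% CI |
|---|---|---|
| 0 | 22/24 = 91.7% | 73.0–99.0 |
| 1 | 21/24 = 87.5% | 67.6–97.3 |
| 2 | 20/24 = 83.3% | 62.6–95.3 |

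The primary result is 22/24 in every row. Only a proportion that the protocol does not define changes.

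**7. Recording length.** Comparing 1 minute (hand-held minimum) with 5 + 5 = 10 minutes (apical) gives 10%, but this sets a minimum against a full schedule. Part B has a 5-minute goal, and its 1-minute minimum for free breathing applies with or without the holder.

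**The case for a change.** The strongest case for the concern is that an analysis plan cannot recover an acquisition fact that was never written down. Part A asks for the position on the case report form and part B does not. The optical record is described as relative and does not show whether a hand or a holder kept the probe in place. Holder use also decides whether the parasternal breath holds are mandatory, so compliance with that rule is hard to check if holder use is not noted.

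Part of this stands. For parasternal-only successes in which breath holds were done, the records named in the protocol do not settle how the probe was held. A tick for holder or hand-held would be cheap and of some interest.

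It does not amount to an error. The case report form is not shown and may hold the field. Part B is a shortened repeat of part A: it also drops the sentences on visual monitoring of image quality and on optical localization. Reading each omission as a different rule is an inference. Position and recording length should be obtainable from the archived session records. The primary objective in section 2.1 is image quality in arrhythmia patients, and a holder-fixed proportion is not among the stated objectives.

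**Conclusion.** The concern does not hold. A hand-held parasternal view can decide a primary success and place the virtual probe, but that is consistent with an early feasibility study of image quality. Followed as written, the protocol gives a sound primary proportion and valid secondary scores.

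The number of successes resting only on a hand-held view is unknown and may be 0. It cannot exceed the number of parasternal-only successes, which the required scoring yields. Each such patient would shift a holder-only figure by 1/24 = 4.2 points and leave the primary result unchanged. What remains is a wish for one more descriptive item, which the case report form or the analysis plan may already cover.

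This rests on three assumptions: the apical probe is always fixed as part A says; per-view scores are kept, as section 2.2 implies; and session records for the parasternal view include localization data, as the general list in section 2.4 suggests.
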